## 7.5 MEASURES OF CHILD DEVELOPMENT

## 7.5.1 Language development

A brief pictorial measure of children's language will be used to assess children's vocabulary. The assessment involves the researcher saying a word (e.g., animals, toys, emotions) and the child being asked to select a picture that best illustrate the word's meaning. The assessment takes 10-15 minutes to administer.

Healthy Start, Happy Start: Long-term follow-up - Study Protocol v 1.2

#### 7.5.2 Executive functions

Children's executive functions will be assessed using a set of brief and engaging computerised tasks. These game-like assessments will measure children's capacity for skills such as inhibition and attention shifting.

#### 7.5.3 Prosocial behaviour

Children's prosocial behaviour will be assessed using a dolls play activity. The child will be asked by the researcher to tell some stories using dolls and props. This task is designed to provide an index of the child's prosocial behaviours and their representations of their behaviour. Recordings will be coded using a standardised rating scale by raters blind to group allocation.

## 7.5.4 School enjoyment

The extent to which children enjoy school will be assessed using a small number of questions related to school enjoyment (e.g., How much do you like going to school? *I like it a lot, I like it a bit* and *I don't like it*).

#### 8 SAFETY REPORTING

In this study, we will adopt a risk proportionate approach to safety monitoring, to ensure reporting is appropriate and useful for the research and participants. Participating families will not receive any intervention as part of their participation in this follow-up research assessment. The intervention tested in the original HSHS intervention (delivered to half of participating caregivers between 2015-2017) was supportive in nature, brief (6 home-based sessions), and delivered at least five years before the families will be followed up in the current study. It is highly unlikely that any serious adverse events seen in the current study would be related to the intervention delivered as part of the original HSHS trial. Because of this, only AEs and SAEs related to study procedures undertaken as part of the follow-up assessment will be monitored and collected.

All members of the research team with direct contact with participants will be trained in procedures and standards for safety reporting. Judgements around the categorisation and seriousness of these events will be discussed with the Study Manager and/or the co-Chief Investigators.

#### 8.1 Definitions

Term	Definition
Adverse Event (AE)	An AE is any untoward medical occurrence which does not necessarily have a causal relationship with the study's procedures. An AE can therefore be any unfavourable and unintended sign (including an abnormal laboratory finding), symptom, or disease temporally associated with the research assessment, whether or not considered related to the study's procedures.
Serious Adverse Event (SAE)	
 
An SAE is defined as any adverse event that:
 
Results in death
 
Is life-threatening*
 
Requires hospitalisation or prolongation of existing inpatient's hospitalisation**
 

Healthy Start, Happy Start: Long-term follow-up - Study Protocol v 1.2

Healthy Start, Happy Start: Long-term follow-up	Protocol No: 1.2	Sponsor: University of Cambridge	V 1.2[tbc]
--	------------------	----------------------------------	------------

	
 
Results in persistent or significant disability or incapacity
 
Is a congenital abnormality or birth defect ***
 

	* "Life-threatening" in the definition of "serious" refers to an event in which the participant was at risk of death at the time of the event; it does not refer to an event which hypothetically might have caused death if it were more severe.
	** "Hospitalisation" means any unexpected admission to a hospital department. It does not apply to scheduled admissions that were planned before study inclusion or visits to an accident and emergency department (without admission).
	*** "Congenital abnormality or birth defect" will not be applicable for this study as all participants will be children aged 6-9 years old and their parents/caregivers.
	Medical judgement should be exercised in deciding whether an adverse event is serious in other situations. Important adverse events that are not immediately life-threatening, or do not result in death or hospitalisation but may jeopardise a participant or may require intervention to prevent one of the other outcomes listed in the definition above should also be considered serious.
Related and Unexpected Serious Adverse Event	A Related and Unexpected Serious Adverse Event is an Adverse Event that is classed as serious, believed with reasonable probability to be due to the study assessment, based on the information provided, and is unexpected.

## 8.2 Severity of Adverse Events

Severity of AEs will be assessed according to the following definitions:

Category	Definition
Mild	Awareness of event but easily tolerated
Moderate	Discomfort enough to cause some interference with usual activity
Severe	Inability to carry out usual activity, including play for infants and children

# 8.3 Causality of Adverse Events

Causality of AEs, i.e., relationship to the study procedures, will be assessed according to the following definitions:

Healthy Start, Happy Start: Long-term follow-up - Study Protocol v 1.2

Category	Definition
Unrelated	No evidence of any causal relationship
Related	There is evidence to suggest a causal relationship between study procedures and the event. The influence of other contributing factors is unlikely or can be ruled out.

## 8.3.1 Recording and reporting of SAEs

The safety reporting period for this study is defined as beginning at the start of the study visit and ending at the completion of research activities. If a participant spontaneously reports relevant safety information following the completion of research activities, that appears to be related to study procedures, this will also be reviewed and recorded where necessary.

All SAEs will be recorded on the Serious Adverse Event Form via the eCRF and emailed to the Sponsor within 24 hours of the research staff becoming aware of the event.

For each SAE the following information will be collected:

- full details in medical terms and case description
- event duration (start and end dates, if applicable)
- action taken
- outcome
- seriousness criteria
- causality (i.e. relatedness to study procedures), in the opinion of the investigator
- whether the event would be considered anticipated. Note, in this study, there are no 'anticipated SAEs' so all occurrence of SAEs would be considered unexpected.

All reported SAEs will be reviewed by the co-Chief Investigator(s) (or designee) within two working days of receiving notification of the SAE report. The SAE review will be recorded on the eCRF. Any change of condition or other follow-up information should be emailed to the Sponsor as soon as it is available or at least within 24 hours of the information becoming available. Events will be followed up until the event has resolved or a final outcome has been reached.

All Related and Unexpected Serious Adverse Events will be notified to the Research Ethics Committee (REC) and the Sponsor within 15 days of becoming aware of the event. Follow up of participants who have experienced a Related and Unexpected Serious Adverse Event should continue until recovery is complete or the condition has stabilised. Safety reporting will be included in the progress report sent to the REC, on the anniversary of ethics approval.

## 9 STATISTICS AND DATA ANALYSIS

A detailed statistical analysis plan will be prepared and signed off by the Chief Investigators and study statisticians prior to any analyses being conducted.

Healthy Start, Happy Start: Long-term follow-up - Study Protocol v 1.2

## 9.1 Sample size and power considerations

The original HSHS trial randomised 300 children; 294 (98%) had at least one post-baseline measurement and will be included in the follow-up analysis. With 294 children and assuming 85% (n = 256) retention at 5-year follow-up, we expect to obtain a posterior probability for superiority of VIPP compared to usual care in the region of 93% if the intervention effect observed at 2 years is sustained at 5 years (ES = 0.22). If the intervention effect is diminished by 50% (ES = 0.11) or completely diminished (ES = 0.0), the probability for superiority of VIPP will be in the region of 78% and 48% respectively. These probabilities will provide valuable evidence to make judgments on the impact of early intervention and whether it is sustained long-term.

## 9.2 Data analysis

The primary estimand will be the treatment policy estimand. The primary analysis will follow an intention-to-treat principle and will include all participants randomised with at least one post baseline measurement (98%, n = 294) in the longitudinal model. The number and proportion lost to 5-year follow-up will be reported with reason where known. All missing outcome data will be summarised by group and time point. Baseline data and outcome data will also be summarised by group and time point. Suitable descriptive statistics will be calculated for continuous variables (means and standard deviations, or medians and inter-quartile ranges) and frequencies and proportions for categorical variables. No between group testing will be performed on variables at baseline as any imbalance will be due to chance and will not invalidate the inference from the trial (38, 39).

The primary aim is to estimate the probability that VIPP-SD is superior to usual care at 5 years post randomisation. A Bayesian mixed effects linear regression model will be used to calculate the probability that the PACS primary outcome score in the VIPP-SD group is greater than in the usual care group. The primary outcome at 5M, 24M and 5 years will be standardised in order to make Pre-PACS and PACs comparable in the model. The model will include treatment group, time, group by time interaction, baseline Pre-PACs score, the randomisation stratification variable center, and subject random effect (intercept and slope). Alongside the probability of superiority for VIPP, we will report the standardised between-arm mean difference with 95% credible interval. No multiple imputation will be used as 98% of the randomised sample will be included in the analysis model and the analysis is valid under a missing at random (MAR) assumption. This assumes the probability of missing data occurring is not dependent on the values of unobserved data, instead it is conditional on the observed variables included in the analysis models. We will perform a sensitivity analysis to the primary analysis to examine the MAR assumption using controlled multiple imputation. With controlled imputation we can induce missing not at random (MNAR) using a  $\delta$  approach (40). The parameter levels used for  $\delta$  will be pre-specified in the statistical analysis plan after discussion with the clinical team, likely values examined will correspond to +/- 25% and 50% of the treatment effect applied to those missing in both arms then each arm in turn to examine the possibility of the missing being informative in one arm only.

A supplementary analysis to the primary analysis will be performed in order to estimate the intervention effect in those that 'complied' (received four or more sessions of VIPP-SD) using a complier average causal effect (CACE) analysis. We will use either the calculation in a Bayesian framework guided by Imbens & Rubin (41) or the use of a two-stage least squares instrumental variable regression approach (42).

Healthy Start, Happy Start: Long-term follow-up - Study Protocol v 1.2

IRAS: 310487

V 1.2[tbc]

Protocol No: 1.2

Sponsor: University of Cambridge

V 1.2[tbc]

A second analysis on the primary endpoint of this follow-up study (PACS at 5 years) using a Bayesian linear regression model with an informative prior distribution on the treatment effect model parameter will also be conducted. The informative prior distribution will be constructed based on the Pre-PACs results in the original trial using data and clinical judgment to translate to an approximate PACs distribution. Missing data will be imputed to allow all original participants to be included in the model. The results from this model will provide information of the difference between arms on the original PACs scale.

Analysis of continuous secondary outcomes will follow the principle of the primary analysis and use a Bayesian analysis with uninformative prior on the treatment effect. Where secondary outcomes are only collected at one time point (5-year follow up) multiple imputation will be used to include all randomised participants. The multiple imputation model will include the variables in the primary model and outcome and other variables as advised by the clinical study team. Where outcomes are repeatedly collected and the same we will use a Bayesian mixed effects longitudinal model. Probabilities for superiority of ViPP as well as treatment effect estimates and 95% credible intervals will be reported for all timepoints (5M, 12M and 5yrs). The results will be displayed visually to display the intervention effect and uncertainty around that estimate over time.

Binary and count outcomes will follow a similar principle for model covariate adjustment and imputation and with use of logistic and negative binomial regression models. CACE analysis will also be repeated for all secondary outcomes to obtain an estimate of the intervention effect in those that received it.

Issues with the availability and completeness of data obtained through data linkage are anticipated. Impacts of the COVID-19 pandemic mean that delays in accessing this data and a greater degree of missing data are likely. With these issues in mind, the main analysis of data will focus on data collected directly from participants. Secondary data analysis will be conducted on the routinely collected data accessed through the National Pupil Database and NHS Digital as an exploratory outcome if and when it becomes available. The exploratory analysis will follow the same principle of the secondary outcomes to compare between arm differences using adjusted regression modelling.

If acquired within the timeframe of the study, the availability of routinely collected data will allow us to examine additional health and education outcomes. Those for educational attainment will be examined in a longitudinal model for the years available and the analysis will be undertaken using a proportional odds model. School absences will be treated as a continuous variable taking account of the observation period for each child. The number of children with school exclusions and categories of special education needs will be tabulated by arm with no formal between arm comparison. We will also compare how both the usual care and intervention arm compare to their peers on the educational data collected. Similar analyses will be undertaken for routine health data if it becomes available within the required timeframe. Specifically, between arm comparisons will be made for children's hospital admissions and attendance at accident and emergency and outpatient appointments.

All descriptive analysis, statistical models, multiple imputation models, and  $\delta$ 's for controlled multiple imputation will be contained in a detailed statistical analysis plan (SAP) that will be written and signed off prior to first data extraction.

Healthy Start, Happy Start: Long-term follow-up - Study Protocol v 1.2

Protocol No: 1.2

Sponsor: University of Cambridge

V 1.2[tbc]

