#### 2 OBJECTIVES AND OUTCOME MEASURES

## 2.1 Primary objectives

The aim of the research is to evaluate the long-term (5 years post-randomisation) effectiveness and cost-effectiveness of a brief early parenting intervention (Video-feedback Intervention to promote Positive Parenting and Sensitive Discipline; VIPP-SD), designed to reduce behaviour problems, compared to usual care.

The primary objective is:

To assess whether, compared to usual care in the NHS, a brief parenting intervention (VIPP-SD) leads to long-term lower levels of behaviour problems in young children who are at high risk of developing these problems (5 years post-randomisation – children aged 6-9 years old).

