## 2.1.1 Primary hypothesis

Among children initially recruited at 12-36 months old with high levels of behaviour problems, adding a brief video-feedback parenting intervention (VIPP-SD) to usual care will reduce enduring behaviour problems measured at five years post-randomisation, using the Parental Account of Children's Symptoms (PACS) interview. The hypothesis will be examined in a Bayesian framework which will provide the probability for VIPP-SD being superior to usual care.

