## 2.3 Outcome measures/endpoints

## 2.3.1 Primary endpoint/outcome

Assessment of severity of behaviour problems at five-years post-randomisation (age 6 to 9 years) using a structured interview assessment (Parental Account of Children's Symptoms; PACS) completed with the child's primary caregiver

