## 7 STUDY MEASURES

#### 7.1 MEASURES OF CHILD BEHAVIOUR

## 7.1.1 Parental Account of Children's Symptoms

The Parental Account of Children's Symptoms (PACS) interview (26) is an age-appropriate version of the PPACS (the primary outcome in the original HSHS trial) for assessment of children aged over five years. This is a standardised, investigator-based interview. The PACS, and its agemodified version, have been utilised in a number of epidemiological and intervention studies (27). It is administered by a trained interviewer who scores a series of behaviours on a 4-point rating scale (0-3) against pre-specified criteria for severity and frequency. The PACS has been found to have good psychometric properties demonstrating a two-factor structure and discrimination between hyperactivity and conduct disorder, and good inter-rater reliability (correlations 0.89-0.95) and internal consistency (hyperactivity  $\alpha = 0.89$ ; conduct  $\alpha = 0.87$ ) (27). The PACS has also been found to correlate with clinician observed behaviour and caregiver reported measures and has strong predictive validity for disruptive behaviour 10 years later (27). Such interview measures are the gold standard assessment for psychopathology. They are more objective as they use investigator-based criteria for scoring symptoms and are thus less prone to the parental biases (e.g., knowledge and expectations of child behaviour) seen when using parent-reported questionnaires. Where two parents/caregivers are participating in the trial the PACS will be completed by the parent who identifies as being the primary caregiver.

Healthy Start, Happy Start: Long-term follow-up - Study Protocol v 1.2

Protocol No: 1.2

Sponsor: University of Cambridge

V 1.2[tbc]

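### Section 9.2 defines the primary probability with the inequality reversed: it asks for a greater PACS score under VIPP-SD, while the rest of the protocol defines benefit as a lower one

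*Protocol*

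**What the plan says.** Section 9.2 opens its account of the primary analysis with the aim: "The primary aim is to estimate the probability that VIPP-SD is superior to usual care at 5 years post randomisation". The next sentence makes this operational. The mixed effects model is to "calculate the probability that the PACS primary outcome score in the VIPP-SD group is greater than in the usual care group". Later in the same paragraph the reported result is named again: "Alongside the probability of superiority for VIPP, we will report the standardised between-arm mean difference with 95% credible interval".

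The direction of benefit is set elsewhere in the protocol:

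- Section 2.1 asks whether VIPP-SD "leads to long-term lower levels of behaviour problems in young children who are at high risk of developing these problems".
- Section 2.1.1 states that adding VIPP-SD to usual care "will reduce enduring behaviour problems measured at five years post-randomisation, using the Parental Account of Children's Symptoms (PACS) interview".
- Section 2.3.1 defines the primary endpoint: "Assessment of severity of behaviour problems at five-years post-randomisation".
- Section 7.1.1 says the PACS interviewer "scores a series of behaviours on a 4-point rating scale (0-3) against pre-specified criteria for severity and frequency".

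The only transformation of the score described in section 9.2 is standardisation at each time point, to put Pre-PACS and PACS on a comparable footing. No reverse scoring is mentioned.

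**The concern.** If a higher PACS score means more severe or more frequent behaviour problems, the probability that the VIPP-SD score is greater is the probability that VIPP-SD does worse. That is the complement of what the same paragraph calls superiority.

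The wording matters because section 2.1.1 makes this probability the output by which the primary hypothesis is examined, and no other sentence in the protocol writes superiority as an inequality on the score. A programmer or reader who takes the sentence at its word gets one minus the intended result. If the SAP has the direction right and the protocol does not, the two documents disagree on the primary quantity.

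**Working it through.** **1. Which way does PACS run?** No sentence in the protocol says that a higher score is worse, so this is an inference. Section 7.1.1 scores each behaviour 0 to 3 for severity and frequency, section 2.3.1 calls the endpoint severity of behaviour problems, and sections 2.1 and 2.1.1 define benefit as lower or reduced problems. These agree, and nothing in the protocol points the other way. Standardising subtracts a mean and divides by a positive SD, so it keeps the order of the scores.

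**2. Which direction do the protocol's own figures use?** Section 9.1 gives the expected posterior probability of VIPP-SD superiority as 93%, 78% and 48% for effect sizes of 0.22, 0.11 and 0.0. It rises with benefit. The probability of a lower score under VIPP-SD does this. The probability of a greater score would fall as benefit grows.

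**3. Approximate reproduction of those figures.** Inputs from the protocol: 256 children at 5 years (section 9.1) and 1:1 allocation (section 3). Assumptions: a flat prior, a normal approximation, and a correlation r between the 5-year score and the earlier measures. The protocol does not give r.

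- SE of the standardised difference = (2/√N) × √(1 − r²). With N = 256, 2/√256 = 0.125.
- Expected posterior probability that the difference favours VIPP-SD = Φ(ES / (SE × √2)).
- Worked case, r = 0.55: SE = 0.125 × √(1 − 0.3025) = 0.1044. At ES 0.22, Φ(0.22 / (0.1044 × 1.414)) = Φ(1.49) = 93.2%.

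| Assumed r | SE | ES 0.22 | ES 0.11 | ES 0 |
|---|---|---|---|---|
| 0 | 0.125 | 89.3% | 73.3% | 50% |
| 0.5 | 0.1083 | 92.5% | 76.4% | 50% |
| 0.55 | 0.1044 | 93.2% | 77.2% | 50% |
| 0.6 | 0.1000 | 94.0% | 78.2% | 50% |
| Stated in 9.1 | – | 93% | 78% | 48% |

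With r between 0.5 and 0.6, the lower-is-better direction comes within 2 points of all three stated figures. With r = 0 it does not, so this is a plausible reconstruction and not an exact reproduction.

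**4. The same scenarios under the literal wording**, the probability that VIPP-SD minus usual care is above 0:

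| | ES 0.22 | ES 0.11 | ES 0 |
|---|---|---|---|
| Complement of the stated figures | 1 − 0.93 = 7% | 1 − 0.78 = 22% | 1 − 0.48 = 52% |
| Approximation, r = 0.5 to 0.6 | 7.5% to 6.0% | 23.6% to 21.8% | 50% |

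The reversal does not depend on r. For any r, the two directions sum to 100%.

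**The case against.** The strongest reply is that nobody would be misled. The sentence before sets the aim as superiority, the same paragraph later reports a probability of superiority, section 2.1.1 says the framework will give the probability that VIPP-SD is superior, and the section 9.1 figures fit only the beneficial direction. The mean difference and its credible interval are reported alongside, so a favourable difference beside a 7% probability of superiority would look wrong at once. Sections 9 and 9.2 also promise a detailed, signed-off SAP, which is not at hand here and may already have the direction right.

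Most of this stands. It shows that the intended quantity is recoverable and that this is a slip of wording. It does not make the sentence correct. The inconsistency with the mean difference would only show once results exist, and a correct SAP would still conflict with the protocol.

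Two stronger readings are tempting, and the protocol does not support either. A reader might infer that the trial plans to headline the probability that VIPP-SD is worse. The surrounding text rules that out as the intention. A reader might also infer that the secondary outcomes inherit the error, since their scales run in both directions. But section 9.2 speaks there only of superiority, which is not tied to a numerical direction. The protocol also gives the direction for most of the scales: SDQ in 7.1.2, PHQ-9 in 7.4.1, RDAS in 7.4.3, BPSES in 7.4.4, and CBCL and parental sensitivity through the hypotheses in 2.2.1. A list of favourable directions by outcome is normal SAP detail.

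**Conclusion.** The concern holds as an internal contradiction in the definition of the primary posterior quantity. The word *greater* in section 9.2 is incompatible with its own paragraph, with the objective and hypothesis, with the scoring of PACS and with the sample-size figures. It is most likely a drafting error and not a flaw in the design or the model.

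Its size is conditional. Only if the sentence is programmed or read literally does a result expected at about 93% appear as about 7%, and one expected at 78% as 22%. Whether that would happen cannot be judged without the SAP. The conclusion rests on one inference, that a higher PACS score is worse, which every relevant section supports. It needs no assumption about correlations or priors.

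**What to change.** Reword the sentence in section 9.2 so that the model is used to calculate *the posterior probability that the mean standardised PACS score at 5 years is lower in the VIPP-SD group than in the usual care group (VIPP-SD minus usual care < 0)*. Check that the SAP and the analysis program use the same direction for this probability, and settle it before the first data extraction so that the correction cannot look like a change made after seeing results.

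The cost is one sentence in the protocol and a matching check of the SAP and code. The model, sample size and data collection are unaffected, and there is no scientific downside.
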